## SAMPLE SIZE CALCULATION

Sample size calculation was based on the comparison of two means derived from the effects of tocotrienol on fatty liver index (FLI) in patients with non-alcoholic fatty liver disease (NAFLD) (21). This is because the effectiveness of tocotrienol in alcoholic hepatitis has not been evaluated previously.

Formula of calculating sample size in clinical trial (22):

$$n = [(Z\alpha/2 + Z\beta)^2 \times \{2(\sigma)^2\}] / (\mu_1 - \mu_2)^2$$

Where:

$n$  = sample size required in each group

$\mu_1$  = mean of FLI for tocotrienol group = 12.82  $\mu_2$  = mean of FLI for placebo group = 3.86

$\sigma$  = standard deviation = 7.0

$Z\alpha$ : This depends on level of significance, for 5% this is 1.96  $Z\beta$ : This depends on power, for 80% this is 0.84

$$n = [(1.96 + 0.84)^2 \times \{2(7.0)^2\}] / (12.82 - 3.86)^2$$

The sample size calculated is 10 per group. Taking into account 20% of subjects might be lost to follow up, the number of each group is adjusted to 13. Hence, the total sample size required for this study is 26 individuals.

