### **STATISTICAL ANALYSIS**

Normality of the data will be assessed through Shapiro-Wilk test. Since the study adopts a time x group design, mixed-design ANOVA will be used to compare the effects across time (within group) and between treatment groups. Small effect analysis will be used as the pairwise post hoc analysis. If the data is skewed, the data will be analysed with Kruskal Wallis test and Mann Whitney U-test with Bonferroni correction for type-1 error. All analyses will be performed using Statistical Package for Social Sciences version 23 (IBM, Armonk, USA). The data will be presented as mean (standard deviation). A p-value less than 0.05 is considered statistical significance.

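### Ten completers per group give about 77% power, not 80%, for a two-sample t comparison of FLI at one visit, because the sizing formula treats the SD as known

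*Protocol*

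**What the plan says.** In the protocol, Sample Size Calculation, the basis is given as "Sample size calculation was based on the comparison of two means derived from the effects of tocotrienol on fatty liver index (FLI") in a published NAFLD trial. The inputs are "mean of FLI for tocotrienol group = 12.82", "mean of FLI for placebo group = 3.86" and "standard deviation = 7.0". The quantile for significance is described as "This depends on level of significance, for 5% this is 1.96" and the one for power as "This depends on power, for 80% this is 0.84". The section then states "The sample size calculated is 10 per group" and raises this to 13 per group, 26 in total, for 20% loss to follow-up.

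The Primary Outcome Measures section lists the between-group difference in FLI at 3 and at 6 months, so a two-arm comparison at one visit is among the planned comparisons. The Withdrawal criteria section says that withdrawn subjects will not be replaced, and that data from subjects who choose to stop will be discarded. The Statistical Analysis section plans a mixed-design ANOVA (time by group) and, for skewed data, Kruskal-Wallis and "Mann Whitney U-test with Bonferroni correction for type-1 error".

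**The concern.** A formula built on 1.96 + 0.84 assumes a known SD. None of the planned analyses does. In a large trial the difference is negligible, but at 10 per group the t distribution on 18 degrees of freedom has visibly heavier tails: the two-sided 5% critical value is 2.101 rather than 1.960. The approximation therefore overstates power.

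The 80% is the only power figure in the protocol, and 10 completers is the number it treats as enough. The extra three per group are a loss allowance, and data from subjects who choose to stop are not kept. If 10 per group falls short of 80%, the chance of missing the planned FLI effect is larger than the reader is told.

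**Working it through.** **Inputs, all from the Sample Size Calculation section.** Means 12.82 and 3.86, so the difference is 8.96; SD 7.0; two-sided 5%; target power 80%; 10 completers and 13 enrolled per group. The standardised difference is 8.96 / 7.0 = 1.28. I take 7.0 to be the SD of the quantity compared, as the formula implies.

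**Step 1. Reproduce the plan.**
n = (1.96 + 0.84)² × 2 × 7.0² / 8.96² = 7.84 × 98 / 80.28 = 9.57, rounded up to 10. With 20% loss, 10 / 0.8 = 12.5, rounded up to 13 per group, 26 in total. The stated figures reproduce exactly.

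**Step 2. Power at 10 per group under the plan's own normal approximation.**
Φ(1.28 × √(10/2) − 1.96) = Φ(2.862 − 1.960) = Φ(0.902) = 81.7%. So 10 per group meets the target if the SD is known.

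**Step 3. Power at 10 per group with the SD estimated.**
Degrees of freedom 10 + 10 − 2 = 18; noncentrality 1.28 × √5 = 2.862; critical value 2.101. The noncentral t distribution gives power 77.2%. The shortfall is 80 − 77.2 = 2.8 points, and the risk of missing the effect is 22.8% rather than 20%.

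**Step 4. Other completer counts, same method.**

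| Completers per group | Power |
|---|---|
| 10 and 10 | 77.2% |
| 10 and 11 | 79.4% |
| 11 and 11 | 81.5% |
| 12 and 12 | 85.0% |
| 13 and 13 | 87.9% |

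Eleven per group is the smallest equal number that reaches 80%.

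**Step 5. Detectable difference.** With 10 per group, 80% power on the t distribution needs a standardised difference of 1.325, and 1.325 × 7.0 = 9.27 FLI points, against the 8.96 planned.

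**Step 6. Allow for random loss.** If completers in each group follow a binomial distribution with 13 subjects and retention probability 0.8, independently between groups, the average power is 78.2%.

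**The case against.** The strongest reply is that nothing has been miscalculated. The protocol cites a standard formula, applies it correctly and rounds up. Using the normal approximation is a choice of method, and the cost is one completer per group. The trial enrols 13 per group, and power is 87.9% if all complete. The inputs also matter more than the choice of quantile: an SD of 7.5 instead of 7.0 would lower t-based power at 10 per group to 71.5%. All of this stands, and it makes the point minor. It does not make the 80% figure right at the sample size to which the protocol attaches it.

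Three stronger readings are tempting, and the protocol does not support them.

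- **A reader might infer that 77% is the power of the planned mixed-design ANOVA.** It is not. With three visits and 10 per group, the group-by-time test has 2 and 36 degrees of freedom, and its power depends on the 3-month effect and the within-subject correlation, neither of which the protocol gives. If 7.0 is taken as the SD of change with compound symmetry, simulated power was about 82% with no effect at 3 months, 69% with half the effect and 81% with the full effect.
- **A reader might infer that the Mann-Whitney branch also falls short, at about 73%.** That value holds for normal data without correction, whereas the plan uses the test only for skewed data and with a Bonferroni correction. For lognormal-shaped data with the same SD and a pure shift of 8.96, simulated unadjusted power was about 84% to 95%. Correction would lower this. In any case, normal quantiles are not what drives a rank test's power.
- **A reader might halve alpha for the two visits, which gives 66% for the t comparison and, with normal data, about 63% for Mann-Whitney.** The protocol does not say over what the Bonferroni correction is taken, and it states none for the ANOVA branch.

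**Conclusion.** The concern holds in a narrow form. On the protocol's own inputs, 10 completers per group give 77.2% power for a two-sample t comparison of FLI at one visit, so the stated 80% is reached only under the known-SD approximation. The arithmetic is correct for the formula cited; the weakness is using that formula at this sample size.

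The size is small: 2.8 points at exactly 10 per group and 1.8 points averaged over random 20% loss, with no shortfall once 11 or more per group complete. The result assumes normally distributed FLI values, a common SD of 7.0 for the quantity compared, and a single unadjusted two-sided 5% test. It supports no statement about the power of the mixed-design ANOVA or of the rank-based fallback.

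**What to change.** Keep 26 patients. In the Sample Size Calculation section, replace the unqualified 80% claim with a sentence such as: *Ten completers per arm give 77% power (two-sample t comparison, two-sided 5%) for an FLI difference of 8.96 with SD 7.0; 80% power needs a difference of 9.3 points or 11 completers per arm.* The section could add that power is 88% if all 13 per arm complete.

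The sentence should name the two-sample t comparison, so that the figure is not read as the power of the mixed-design ANOVA, and it should give no Mann-Whitney or Bonferroni figure. The cost is one sentence and a slightly less favourable power statement. No patients are added, and the analysis does not change.

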## **SCREENING**

Primarily we will be recruiting adult patients who fulfil all the inclusion criteria of this study, who come for follow up in Gastroenterology & Hepatology clinic in Hospital Canselor Tuanku Muhriz UKM (HCTM). Additionally, our research subjects were also recruited from the general public who responded to our recruitment poster in the hospital and on social media platforms. Subjects will answer a questionnaire on their demographic and lifestyle details, medical and medication history. Their alcohol consumption behaviour will be surveyed using the AUDIT questionnaire. A qualified physician will perform physical examination on the subjects. The AUDIT questionnaire (23) is a 10-item screening tool used to identify individuals with harmful drinking behaviour. A score of 8 or more indicates harmful or hazardous drinking behaviour. In addition, patients will be screened for clinical (signs and symptoms of alcoholic liver disease such as parotid swelling, hepatomegaly and clinical evidence of cirrhosis) and biochemical evidence of alcoholic liver disease (transaminitis, AST:ALT ratio >2.0, raised gamma glutamyl transferase (GGT), mean corpuscular volume (MCV) and total bilirubin).

### **Body anthropometry**

Body anthropometry will be performed on every visit. Height of the subjects will be measured using a stadiometer. Body weight of the subjects will be measured using a weighing scale. Body composition of the subjects will be analysed using a 4-point bioimpedance machine. Body mass index of the subjects will be calculated as per the convention.

### **Blood collection**

Blood collection will be performed on every visit. Subjects will be requested to fast for 8 hours before blood withdrawal. Venepuncture will be performed by a qualified phlebotomist. 5 ml of fasting blood will be drawn in the morning.

### **Determination of plasma tocotrienol level (HPLC)**

A portion of the blood will be collected using heparin tubes. Plasma will be extracted and aliquoted into 200 µL. The plasma will be stored in - 70°C until analysis. Upon analysis, the plasma will be thawed, added with 50 µL 95% ethanol containing 10 µg/mL butylated hydroxytoluene, and vortexed vigorously for 5 seconds. Then, 1 mL absolute alcohol will be added to the mixture, which will be remixed before being centrifuged at 1500 g for 15 minutes at 18°C. The pellet will be removed, and the supernatant will be added with 3 mL hexane and mixed vigorously for 5 minutes. The samples will be centrifuged again at 1500 g for 15 minutes at 18°C. The upper layer (2.5 mL) of the supernatant will be removed, placed in new Eppendorf tubes and vacuum evaporated for 40 minutes. The dried residues will be reconstituted in 100 µL HPLC grade hexane, vortexed, and passed through a 0.45 µm filter to remove residual particles. The samples will be collected using an amber vial and analysed by an HPLC machine (Shimadzu RF-10A XL with fluorescence detector) at the excitation wavelength of 294 nm and the emission wavelength of 330 nm. The tocotrienol isomers and alpha- tocopherols will be separated on a 250 mm x 4.6 mm, 5 µm silica column and eluted with a mobile phase of 99:1 (v/v) hexane-isopropanol at 1.5 mL per minutes flow rate. The identity of each compound will be confirmed by co-elution with spiked standard obtained from Excelvite Sdn. Bhd. The peaks will be quantified and integrated using Shimadzu Workstation software.

### **Biochemical assay**

Full blood count, liver profile (AST, ALT, GGT), lipid profile and fasting glucose test will be sent to an accredited laboratory for analysis using automated biochemistry analyser. HepatitisB and C status, as well as antibodies for autoimmune hepatitis will be assayed using an automated immunoassay machine. A portal of the blood will be centrifuged to isolate serum for acetyldehyde, malondialdehyde and inflammatory cytokines. These parameters will be assayed using enzyme-linked immunoassay based on manufacturer protocols.

### **Ultrasound**

Ultrasound of the hepatobiliary system will be performed during initial recruitment to rule out the presence of hepatocellular carcinoma (HCC) which can occur in patients with alcoholic liver cirrhosis. During the screening an ultrasound probe will be placed in the patients' right hypochondrium to assess for any abnormal lesions representative of HCC. It is a non-invasive procedure which takes approximately 20 minutes. Patients with hepatocellular carcinoma will be excluded from the study.

### **Fibroscan**

This is a non-invasive test to measure liver stiffness, kPa (indicator of liver fibrosis) and to detect degree of fat accumulation (CAP range value of 100-400 dB/m). Liver stiffness of > 8kPa indicates advanced fibrosis while CAP of > 263 indicates fatty liver. During the screening, the patient will lie down on the examination bed with his/her right hand behind

his/her head. Investigator will place the probe between the right ribs of the patient. Measurements will be recorded into the machine (FibroScan® 502 Touch). The screening is quick, easy and non-invasive and usually takes less than 15 minutes.

## ALGORITHM OF DIAGNOSIS OF ALCOHOLIC HEPATITIS:

### **Alcohol misuse disorder:**

Regular alcohol consumption > 20g/day in female and >30g/day in males

### **Clinical parameters:**

Ascites (Degree)

Hepatic encephalopathy (West haven criteria)

### **Biochemistry:**

Raised ALT and AST ratio AST: ALT>2.0

Raised mean corpuscular volume (MCV)

Raised gamma glutamyl transpeptidase (GGT)

Raised total bilirubin

Platelets

Coagulopathy: Deranged INR and PT

### **Oxidative markers:**

Acetyldehyde

Malondialdehyde

### **Exclusion of:**

Obese patients (a BMI of a BMI of 30 kg/m^2 or more) and with metabolic syndrome

Patients with bleeding disorders, and on anticoagulant or antiaggregant treatments

Hepatitis B (HBsAg)

Hepatitis C (Anti-HCV)

Autoimmune hepatitis (ANA, AMA, ASMA, IgG)

NAFLD (BMI, fasting glucose, blood pressure, fasting total cholesterol, triglyceride and HDL)

Hereditary hemochromatosis (Ferritin, Tst)

Severe alcoholic hepatitis (Maddrey's discriminant score)

[figure not shown]
### **Assessment of advanced fibrosis/cirrhosis:**

Fibroscan, FibroTest (FT)

### **Radiology:**

Ultrasound of the hepatobiliary system TRO hepatocellular carcinoma

## Randomisation and Treatment

The treatment assigned to participants for 6 months was either mixed tocotrienols 200 mg twice daily or placebo. A treatment period of 6 months will be adopted because only patients with mild alcohol steatohepatitis are recruited, whose condition would resolve within months with alcohol abstinence alone. The content in each capsule of the mixed tocotrienols preparation was 61.5 mg, 112.8 mg and 25.7 mg for alpha-, gamma- and delta-tocotrienol, respectively and 61.1 mg of alpha-tocopherol. Both placebo and tocotrienols, were soft gel capsules and were similar in terms of colour, size, shape and surface texture. Participants were randomised using a computer-generated random allocation sequence. A permuted block design was employed. Each block of specified size contained an allocation ratio of 1:1 (placebo:tocotrienols). The

random allocation sequence would select the next block and determine the next allocations. Sequence was not made known to researchers who enrolled participants. For the purpose of assigning participants to interventions, a subject number was used. The researcher who generated the random allocation sequence and assigned participants was blinded to subjects' clinical data and was independent from the persons who enrolled participants. The mixed tocotrienols preparation and the placebo capsules were purchased from Hovid (Ipoh, Malaysia). Researchers and volunteers were blinded to the assigned treatment.

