### Primary Outcome Measures:

1. Change from baseline in Liver Enzyme Profile (Aspartate Aminotransferase [AST], Alanine Aminotransferase [ALT], and Gamma-Glutamyl Transferase [GGT]) at 3 and 6 months. Measured in units per liter (U/L) and reported as absolute and percentage change. Lower values indicate improved liver function.
2. Between-group difference in Liver Enzyme Profile (AST, ALT, GGT) at 3 and 6 months (Tocotrienol-Rich Fraction vs placebo). Measured in U/L. Lower values indicate improvement.
3. Change from baseline in Fatty Liver Index (FLI) at 3 and 6 months. Unitless score (range 0–100). Higher scores indicate greater hepatic steatosis (worse outcome). Reported as absolute and percentage change.
4. Between-group difference in Fatty Liver Index (FLI) at 3 and 6 months (Tocotrienol-Rich Fraction vs placebo). Range 0–100. Higher scores indicate worse steatosis.
5. Change from baseline in Liver Stiffness Measurement using Transient Elastography (FibroScan® score) at 3 and 6 months. Measured in kilopascals (kPa; typical range 2–75). Higher values indicate greater fibrosis. Reported as absolute and percentage change.
6. Between-group difference in Liver Stiffness Measurement (FibroScan® score) at 3 and 6 months (Tocotrienol-Rich Fraction vs placebo). Measured in kPa. Higher values indicate worse fibrosis.

\*Aspartate aminotransferase (AST) is usually used to detect liver damage. It is often ordered in conjunction with other liver enzymes, alanine aminotransferase (ALT) and gamma-glutamyl transpeptidase (GGT), or as part of a liver panel or comprehensive metabolic panel (CMP) to screen for and/or help diagnose liver disorders. The changes in these liver enzymes can also be used to monitor the compliance of patients toward alcohol abstinence.

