### **Exclusion criteria:**

1. Severe alcoholic hepatitis defined as Maddrey's discriminant function  $>32$
2. Patients with other concomitant liver diseases:
  - a. Hepatitis B
  - b. Hepatitis C
  - c. Non-alcoholic fatty liver disease (NAFLD)
  - d. Autoimmune hepatitis (AIH)
  - e. Hereditary hemochromatosis
3. Patients who are obese (a BMI of  $30 \text{ kg/m}^2$  or more) and with metabolic syndromes
4. Patients with bleeding disorders and who have been on anticoagulant or antiaggregant treatments
5. Patients who have been on corticosteroid therapy or pentoxifylline for alcoholic hepatitis
6. Patients with hepatocellular carcinoma
7. Pregnant patients
8. Patients who are breastfeeding
9. Patients with Childs C liver cirrhosis
10. Patients who have pyridoxine allergy or history

11. Patients who are judged by investigator that participation of the study is difficult due to disease as follow; hepatic cirrhosis, Wilson's disease, malignant tumor, serious metabolic disease, severe renal disease, severe pulmonary disease, severe cardiovascular disease, severe nervous disease/psychiatric disorder, muscle disease and etc
12. Patients taking vitamin E, herbal supplements, or other investigational products within 90 days prior to the participation in the study.
13. Patients who have been taken any medications that could affect the treatment: hypoglycemic agents, colchicine, penicillamine, corticosteroids, ursodeoxycholic acid, pentoxifylline, long-term use of NSAIDs, statins, neuroleptics, anticonvulsant medications, high-dose acetaminophen( $\geq 2.5$ g/day)
14. Patients who have received treatment that may affect liver function within 1 month prior to the participation in the study
15. Patients who could not comply with alcohol abstinence.
16. Patient who considered ineligible for participation in the study as Investigator's judgment

**Note:** Patients enrolled in this study MUST abstain from alcohol consumption throughout the study period

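### Primary outcomes 1, 3 and 5 read as within-arm changes, which cannot show a TRF effect when abstinence alone is expected to resolve the disease; the between-arm contrast of change is not named as the efficacy test

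*Protocol*

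**What the plan says.** Under Primary Outcome Measures the protocol lists six items in three pairs.

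- Items 1, 3 and 5 are "Change from baseline in Liver Enzyme Profile", "Change from baseline in Fatty Liver Index (FLI) at 3 and 6 months" and "Change from baseline in Liver Stiffness Measurement using Transient Elastography". None names a comparator.
- Items 2, 4 and 6 are the matching comparisons of arms, for example "Between-group difference in Liver Enzyme Profile (AST, ALT, GGT) at 3 and 6 months (Tocotrienol-Rich Fraction vs placebo). Measured in U/L" and "Between-group difference in Fatty Liver Index (FLI) at 3 and 6 months (Tocotrienol-Rich Fraction vs placebo". Each is stated at 3 and 6 months in the units of the measure, with no reference to the baseline value.

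A footnote there adds that the enzyme changes may also serve to monitor abstinence.

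The Statistical Analysis section calls the design time x group and states that "mixed-design ANOVA will be used to compare the effects across time (within group) and between treatment groups". Rank tests replace this if the data are skewed. The section does not say which term or contrast carries the efficacy conclusion.

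On the expected course of disease, Randomisation and Treatment justifies the six-month period by recruiting mild steatohepatitis "whose condition would resolve within months with alcohol abstinence alone". The note closing the exclusion criteria says "Patients enrolled in this study MUST abstain from alcohol consumption throughout the study period". The rule therefore binds both arms.

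**The concern.** The protocol itself predicts that patients on placebo will improve. A fall in enzymes, FLI or stiffness in the TRF arm is then what an inert capsule would produce. Change from baseline nevertheless stands as a primary outcome in its own right beside the comparison with placebo, and the analysis section tests over time within group. The hypotheses are worded as TRF reducing or normalising each measure, so a significant fall in the TRF arm could be reported as a primary result in support of them.

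A second, smaller matter is how the between-arm outcomes are fixed. As worded they compare levels after baseline. With 10 to 13 per arm, the arms can differ noticeably at baseline by chance, and the baseline measurement already planned would deal with that.

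**Working it through.** **Inputs.** From Sample Size Calculation: FLI means 12.82 (tocotrienol) and 3.86 (placebo), SD 7.0, two-sided 5%, power 80%, 20% loss. Not in the documents, hence assumed: that 7.0 is the SD of change and 3.86 a change; the correlation rho between baseline and follow-up; compound symmetry; and how much of the effect is present at month 3. FLI is scored so that higher is worse, so 12.82 against 3.86 favours tocotrienol only if both are reductions. This makes the change reading plausible, but the protocol does not say so.

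**The plan's own figure.** n = (1.96 + 0.84)² x 2 x 7.0² / 8.96² = 9.57, rounded up to 10. Then 10 / 0.8 = 12.5, rounded up to 13 per arm, 26 in all. It reproduces.

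**Within-arm test with no treatment effect.** Both arms fall by the same amount. The paired t test in one arm has noncentrality fall / (7/√n) on n − 1 df.

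| Common fall | n = 10 | n = 13 |
|---|---|---|
| 3.86 | 1.74, significant in 34% | 1.99, 45% |
| 7 | 3.16, 80% | 3.61, 91% |
| 8.96 | 4.05, 95% | 4.62, 99% |

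At a fall of 3.86, the pattern of TRF significant and placebo not arises with probability 0.345 x 0.655 = 0.23 (n=10) or 0.448 x 0.552 = 0.25 (n=13). All these figures are per measure and per visit.

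**Between-arm test at month 6.** Difference 8.96, 10 per arm. With SD of change 7, the SD of a level is 7/√(2(1 − rho)) and the ANCOVA residual SD is that times √(1 − rho²). Two-sample t on 18 df (17 for ANCOVA):

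| rho | SD of level | ANCOVA SD | Power, levels | Power, change | Power, ANCOVA |
|---|---|---|---|---|---|
| 0.3 | 5.92 | 5.64 | 89% | 77% | 92% |
| 0.5 | 7.00 | 6.06 | 77% | 77% | 88% |
| 0.7 | 9.04 | 6.45 | 55% | 77% | 83% |
| 0.8 | 11.07 | 6.64 | 40% | 77% | 81% |

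Levels do better than change below rho 0.5 and worse above it. ANCOVA has the most power in every row. If 7.0 is instead the SD of a level, levels have 77% at every rho.

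**Time x group interaction of the mixed ANOVA, with baseline as one of the visits.** Error variance is 7²/2 = 24.5; lambda = (n/2) x Σ(d_j − mean d)² / 24.5; F on 2 and 36 df.

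- Arm differences 0, 4.48, 8.96 (half the effect at month 3): lambda = 5 x 40.14 / 24.5 = 8.19, power 69%.
- Arm differences 0, 8.96, 8.96 (full effect at month 3): lambda = 5 x 53.52 / 24.5 = 10.92, power 82%.

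The group main effect averages in the pre-treatment visit. In the first case the contrast it tests is (0 + 4.48 + 8.96)/3 = 4.48, half the month-6 difference.

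**Chance imbalance.** The probability of a baseline difference above 0.5 SD is 2(1 − Φ(0.5/√(2/n))): 26% with 10 per arm, 20% with 13. In 20,000 simulated null trials (10 per arm, rho 0.7), overall type I error was about 5% for month-6 levels and for change. Among trials with imbalance above 0.5 SD it was 13% for levels, 18% for the group main effect, 8% for change and 5% for ANCOVA.

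**The case against.** Change from baseline names a metric, and the protocol never says that items 1, 3 and 5 are judged within one arm. The trial is double-blind and placebo-controlled, its sample size compares two arm means, and every measure has its own TRF-versus-placebo outcome. All of that is correct. A reader might infer that the plan declares success on a within-arm p-value, or that an inert product would meet half the primary outcomes; the document contains no such success rule. What remains is that the comparison with placebo is already listed separately, so items 1, 3 and 5 add nothing unless read within arm, and the analysis section expressly compares over time within group.

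A reader might also infer that the analysis ignores baseline, or that the comparison that tests TRF is the least efficient available. Neither is supported. If baseline is one of the visits, the time x group interaction compares change between arms and so uses baseline. The ranking of levels against change depends on a correlation the documents do not give and reverses at 0.5, so the 40% and 55% figures are not properties of this protocol. Randomisation keeps the unadjusted comparison valid. The choice of covariate may properly sit in a statistical analysis plan that is not shown. The list of primary outcomes, however, is fixed in the protocol.

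**Conclusion.** The point about within-arm change holds and should be settled before any data are analysed. Given the protocol's own expectation of recovery on abstinence in both arms, a fall from baseline in the TRF arm is not evidence for TRF. The 34% to 45% (fall of 3.86) and 80% to 91% (fall of 7) are illustrations that rest on 7.0 being the SD of change. The conclusion itself does not depend on them.

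The point about baseline is narrower. Outcomes 2, 4 and 6 are worded as post-baseline differences. The interaction, which does use baseline, is not named as decisive, and the group main effect is diluted by the pre-treatment visit. This affects precision and sensitivity to chance imbalance, not average bias. Over the correlations tabulated, adjustment for baseline gives 81% to 92% power against 77% for unadjusted change and about 69% to 82% for the interaction.

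**What to change.** 1. Make outcomes 1, 3 and 5 descriptive summaries within each arm, not primary outcomes.
2. Define outcomes 2, 4 and 6 as the between-arm difference in change from baseline, estimated with the baseline value as covariate: ANCOVA, or a mixed model with the post-baseline visits as response and terms for arm, visit, arm x visit and baseline x visit.
3. State in the Statistical Analysis section that efficacy conclusions rest only on this between-arm contrast, and that neither a within-arm p-value nor the group main effect over all visits is evidence for TRF.

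The cost is protocol wording. The baseline values are already planned and SPSS, the named package, fits these models. No extra patients are needed: the protocol's formula with the ANCOVA SD gives 8, 9, 9 and 10 per group at rho 0.5, 0.7, 0.8 and 0.9, within the planned 10 evaluable per arm.
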